Initially, many surgeons used larger catheters (22Fr) to promote an open anastomosis, but some groups have found this to be associated with fossa navicularis strictures⁷. As a result, most surgeons now leave an 18 or 20 French Foley catheter to drainage for approximately 1 week post-operatively⁷. Interestingly, no study to our knowledge has assessed whether catheter size has an impact on continence, post-operative pain, and long term complication rates such as bladder neck contracture. We would expect urinary flow rates to differ based on urethral or catheter diameter according to Poiseuille's law, and several studies have shown this to be the case⁸.

In this study, we will randomize our RALP patients to either a 16 French or 20 French catheter to assess the effect of catheter size on post-operative catheter pain. Additionally, we will investigate pads per day, urinary flow rates, post-void residual urine volume (PVR), International Prostate Symptom Scores (IPSS) and Quality of Life (QoL) score, as well as long term complications. We hypothesize that patients with a smaller catheter will have improved pain scores and less opioid use. In terms of return to continence, we predict that use of a smaller urethral catheter will decrease flow rates and consequently protect against urinary leakage without higher risk of urinary retention. We expect this group to use less pads per day at the 6 week post-operative visit. We do anticipate a higher risk of bladder neck constriction (BNC) would be expected as well in the long term given the smaller diameter anastomosis.

Study Purpose and Objectives

The purpose of this clinical study is to assess the effect of catheter size on post-operative catheter pain, urinary continence, urinary flow rates, PVR, IPSS and QoL scores, as well as long term complications. The details of data collection are described in the "Data Collection Procedures" section below. Study objectives will be measured by:

Primary Outcome:

- Mean catheter related pain score on POD5-7

Secondary Outcomes:

- IPSS and QoL Scores at 6 and 12 weeks
- Opioid use after discharge until POD7
- Pads per Day at 6 and 12 weeks
- Urinary flow rate at 12 weeks
- PVR at 12 weeks
- Long-term complications at 12 weeks, 1 and 2 years

Risks and Benefits

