- Have a significant deviation from the normal operative protocol such as significant bladder neck reconstruction or conversion to open (these patients will be considered a screen fail during the operation and will not be randomized to a certain catheter size)
- Have a history of pelvic radiation

In addition, patients who have a significant deviation from the normal post-operative course such as pulmonary embolism, myocardial infarction, stroke, or other major complications that are unrelated to study intervention but would impact outcome measures may be excluded from data analysis and further data collection per investigator's discretion.

Patient recruitment

Patients seen in pre-operative consultation by Virginia Mason Medical Center urologists will be assessed by the consulting surgeon for protocol eligibility at the time of consultation. The consent form will be reviewed with the patient in person, or by phone, at least 24 hours prior to surgery to allow time for consideration and questions. Patients may sign the consent anytime in the pre-operative setting before medication has been administered.

Early Termination

Patients may be discontinued from the study, per investigator's discretion, if any of the following conditions are met:

- Catheter remains in place greater than 14 days post operatively
- Lost to follow up (patient cannot be reached to schedule a follow up appointment after 3 attempts)
- Patient withdrawal of consent

Data Collection Procedures

Patient follow-up visits are routine and will occur at approximately 1, 6, and 12 weeks post operatively. Specific time point and methods of data collection are described below:

Post-surgical pain scores will be determined using a visual analog scale (VAS) with patients rating their mean post-operative pain on a scale from 1- No Pain to 10- Worst Possible Pain (Figure 1). Patients will be asked to indicate their pain specifically related to the catheter on this

scale. This information will be collected at POD7 just prior to catheter removal. This will be done in clinic if the appointment is that day or by telephone/mail/email/fax if the patient's appointment is not that day. A post-operative form including the VAS pain scale (Figure 1) and a pre-paid mailing envelop will be given to the patient in their study packet.

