Opioid use will be collected at POD7 using the post operative pain form (Figure 1). Patients will be asked to count the number of pills left in their opioid prescription to determine number of tabs taken from discharge to POD7. If the patient is discharged after POD1, opioids taken as an inpatient on POD2 from the medical record will be included in opioid use. All opioid data will be converted a standardized morphine equivalency for comparison.

Pads per day: The patient will be asked to indicate the number of pads per days they are using. This data will be collected at 6 and 12 week follow up visits. This will be done in clinic if the appointment is that day or by telephone/mail/email/fax/REDCap (patients contact information, including email address, will be obtained from Cerner when available or by asking patient) if the patient's appointment is not that day. We recommend use of the Depend® Incontinence Guard for men (<https://www.depend.com/mens-solutions/products/10544>), or a comparable generic version.

International Prostate Symptom Score (IPSS) and Quality of Life Score: This validated questionnaire is an 8 question (7 symptom questions + 1 quality of life question) written screening tool used to screen for, rapidly diagnose, track the symptoms of, and suggest management of the symptoms of prostate disease. This is a clinician rated, validated scale. It will be administered and scores collected at the 6 and 12 week follow up visits. This will be done in clinic if the appointment is that day or by telephone/mail/email/fax/REDCap (patients contact information, including email address, will be obtained from Cerner when available or by asking patient) if the patient's appointment is not that day.

PVR: Post void residual volumes will be measured by having the patient void to their best effort (into a uroflowmeter described below) and then using a standard suprapubic bladder scanner to measure the remaining urine volume immediately after voiding. This will be measured at the 12 week follow up visit per investigator's discretion if clinically indicated.

Urinary flow rates will be measured by using a uroflowmeter. The patient voids into the device and is records the max flow rate, void time, and voided volume. This will be be measured at the 12 week follow up visit per investigator's discretion if clinically indicated.

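### Flow rate and PVR are listed as secondary outcomes for ANOVA but are measured only when the investigator judges it clinically indicated, so a between-arm test would use a subset selected after randomisation

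*Combined protocol and SAP*

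**What the plan says.** Study Purpose and Objectives gives the aim as assessing "the effect of catheter size on post-operative catheter pain, urinary continence, urinary flow rates, PVR, IPSS and QoL scores", along with long-term complications. Its secondary outcomes include "Urinary flow rate at 12 weeks" and "PVR at 12 weeks", with no restriction to a subset. Treatment Methodology and Statistical Considerations assigns the secondary outcomes to ANOVA.

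Data Collection Procedures attaches a condition to each of the two. For PVR: "This will be measured at the 12 week follow up visit per investigator's discretion if clinically indicated". For flow rate: "This will be be measured at the 12 week follow up visit per investigator's discretion if clinically indicated". The double-asterisk footnote to the Schedule of RALP Study Procedures and Assessments repeats the condition for both.

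The background text before the objectives states a directional expectation: "we predict that use of a smaller urethral catheter will decrease flow rates" and so "protect against urinary leakage without higher risk of urinary retention". Risks and Benefits likewise expects possibly reduced flow with 16Fr.

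**The concern.** The outcome list and the analysis sentence treat flow rate and PVR as comparisons of the randomised arms. The collection rules make them clinical tests for selected patients. For these two outcomes, being unmeasured is allowed by design and is not ordinary dropout.

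If poor voiding prompts the test, selection depends on the outcome. If catheter size changes voiding, as the protocol predicts, selection also depends on arm. If the investigator knows the catheter size, it could depend on arm directly. The measured groups then no longer have the balance that randomisation gave, and their difference in means need not estimate the effect of catheter size. At stake is any comparative statement on flow or PVR.

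**Working it through.** **1. The passages side by side.**

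- *Outcome list and purpose:* both outcomes at 12 weeks, unrestricted.
- *Analysis:* ANOVA for secondary outcomes; no analysis set for flow or PVR.
- *Collection and schedule:* both only if clinically indicated, with no criteria and no requirement that criteria match across arms. No masking is described.
- *Contrast:* IPSS/QoL and pads per day are collected at 6 and 12 weeks with no such condition, and by telephone, mail or other remote means if the appointment falls on another day.
- *Missing data (Data Analyses):* judged individually, with a problem expected mainly in long-term data. This does not anticipate 12-week values left unmeasured by design.

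The conflict follows from the text and needs no numerical assumption.

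**2. How large the bias could be.** The plan has no figure of its own to reproduce: its only sample size (44) is for pain, and it gives no mean, SD or effect for flow or PVR. All inputs below are therefore assumptions, for flow only; PVR was not modelled.

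Inputs: SD 7 mL/s; true means 17 (16Fr) and 20 (20Fr), a true difference of +3.0 (20Fr minus 16Fr). A patient is measured if flow plus normal noise with SD τ falls below a cut-off c. With s = √(7² + τ²) and z = (c − μ)/s, the mean among measured patients is

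μ − (49/s) · φ(z)/Φ(z).

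Example, c = 15 in both arms, τ = 3: s = √58 = 7.616.
- 16Fr: z = −2/7.616 = −0.263; φ = 0.3854, Φ = 0.3964; mean = 17 − 6.434 × 0.972 = 10.74.
- 20Fr: z = −5/7.616 = −0.657; φ = 0.3216, Φ = 0.2557; mean = 20 − 6.434 × 1.258 = 11.91.
- Observed difference: 11.91 − 10.74 = about +1.16 (unrounded means).

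The correlation between trigger and flow is 7/s.

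| Scenario (difference, mL/s) | τ = 3 (corr. 0.92) | τ = 7 (0.71) | τ = 14 (0.45) |
|---|---|---|---|
| True +3.0, indication unrelated to flow | +3.0 | +3.0 | +3.0 |
| True +3.0, cut-off 15 in both arms | +1.16 | +1.94 | +2.59 |
| True +3.0, cut-off 18 (16Fr) v 15 (20Fr) | −0.48 | +0.97 | +2.20 |
| No true difference (20 v 20), cut-off 15 in both | 0 | 0 | 0 |
| No true difference, cut-off 17 v 15 | −1.24 | −0.72 | −0.28 |
| No true difference, cut-off 18 v 15 | −1.84 | −1.06 | −0.41 |

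With a common cut-off of 15, the share of the true difference lost is 1 − 1.16/3 = 61%, 1 − 1.94/3 = 35% or 1 − 2.59/3 = 14%.

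**3. Effect on the test.** Simulation with 22 patients followed per arm (44 split 1:1) and a two-sided 5% t test on the measured patients, results in order τ = 3 / 7 / 14:
- No true difference, 18 v 15: rejects in 10.9% / 6.2% / 5.1%.
- No true difference, 17 v 15: 7.6% / 5.5% / 5.0%.
- No true difference, common cut-off 15: 4.9% / 5.0% / 5.0%.
- True +3.0, common cut-off 15: power 6.7% / 9.4% / 12.2%, against 28.4% if all 22 v 22 are measured.

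**4. Limit under full measurement.** With 22 v 22, the difference detectable at 80% power is (1.960 + 0.842) × √(2/22) = 0.845 SD (normal approximation).

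**The case against.** The strongest case on the other side has four parts.

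*The analysis is not spelled out.* No section says that a measured-only ANOVA will be presented as a randomised comparison. The ANOVA sentence is generic: it also covers long-term complications, although Data Analyses speaks of risk ratios. This stands. The supportable statement is that treatment of unmeasured patients is unspecified and that measured-only analysis is the likely default.

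*The magnitudes are assumed.* A reader might infer from the table that the test will be anti-conservative or the sign reversed. The documents do not support that. Reversal needs cut-offs that differ by arm and a trigger that tracks flow closely (noise SD below about 4.2). The 10.9% rejection rate needs the same combination. Nothing in the documents indicates either. If indication is unrelated to flow, or if arm affects neither flow nor indication, there is no bias in the comparison.

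*Retention need not rest on PVR.* A reader might infer that the retention part of the hypothesis cannot be examined. But under Post Operative Complications, any significant departure from the usual recovery is recorded, in hospital or at clinic visits, with no clinical-indication condition. Retention is not named there, but clinically evident retention plausibly falls within it. This stands, so the point is confined to flow rate and PVR values.

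*The impact is limited.* These are two secondary outcomes without a power claim, and even full measurement gives low power. This is true and bounds the importance, but it does not remove the conflict between the outcome list and the collection rules.

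**Conclusion.** The point holds with high confidence as an internal conflict. The plan names flow rate and PVR as outcomes to be tested between arms but does not ensure that they are measured in the randomised arms. The only available comparison would be of patients selected after randomisation, by a rule that is not described and that the protocol's own flow hypothesis could link to arm.

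The size of any bias is unknown. Under the assumed flow inputs, a common low-flow trigger shrinks a true difference by anything from slightly (14%) to more than half (61%); a false difference arises only if the trigger differs by arm. These figures show direction and are not estimates for this trial.

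The primary pain outcome is not affected. The change should be made because it is cheap and settles what the trial may claim.

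**What to change.** While measurement stays discretionary:

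1. State in Study Purpose and Objectives, and in Treatment Methodology and Statistical Considerations, that flow rate and PVR are descriptive only and are not tested between arms.
2. Report the values with the number measured and the reason for measurement, by arm.
3. State that no between-arm conclusion on flow or PVR will be drawn from them.
4. Mark the flow prediction, in the background text and in Risks and Benefits, as rationale not tested in this trial. Leave the retention prediction to be addressed, if at all, through the complication data.

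Cost: wording changes, one extra recorded item (reason for measurement), and IRB review of the amendment, which the Human Subjects section requires. No patient procedure is added. The downside is that no comparative claim on flow or PVR can be made.

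Alternative, if the sponsor wants to keep both as tested outcomes: reconcile the outcome list, Data Collection Procedures, the analysis text and the schedule so that both are measured in every patient attending the 12-week visit. The visit already exists ("Patient follow-up visits are routine and will occur at approximately 1, 6, and 12 weeks post operatively"), and PVR is scanned straight after the uroflowmeter void. This removes selection by indication, but it adds procedures whose cost the documents do not give, and it also needs IRB review. Power would stay low, and the protocol should say so.

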Post Operative Complications will be recorded during the hospital stay or at clinic follow up visits and include any significant deviation from the normal post-operative course. Transient and permanent complications will be evaluated as part of this trial. At the long term follow up visits at 1 and 2 years, investigators capture long term complications such as bladder neck contracture.

Timing of Data Collection

Follow up visit #1 will occur 7 days +/- 7 following discharge, although as indicated above, pain scores and opioid use will be collected on POD7 regardless of clinic visit day. If the clinic appointment is not on POD7, we will collect this data by telephone or by mail. Timing of catheter

removal will be determined by the surgeon and is not affected by the study. Follow up visit #2 will occur 6 weeks +/- 4 weeks following discharge. Follow up visit #3 will occur 12 weeks +/- 5 weeks following discharge to account for patient availability. Patients will have annual follow-up thereafter and long term complications such as bladder neck contracture (BNC) will be recorded at 1 and 2 years post treatment (+/- 3 months). No other study data will be collected at these long term follow up visits. The specifics of how data will be collected and analyzed for each outcome are listed below.

Duration of Study participation

It is estimated that each patient who enrolls in the study and completes the routine follow-up visits will be participating for approximately two years.

Treatment Methodology and Statistical Considerations

Patients will be randomized by chance to either a 16 French or 20 French catheter in a 1:1 ratio. Subjects will be randomly assigned to either the standard of care or multi-modal group using Microsoft Excel ® randomization function.

A 2 year follow-up was chosen to allow for transient postoperative abnormalities to resolve so that the incidence of both transient and permanent complications can be evaluated.

Statistical evaluation of this study was completed by Axio during protocol development to ensure proper design and statistical power. We will use an ANOVA statistical variance model to test the hypothesis that the 20Fr group will have a higher mean pain score than the 16 French group. Secondary outcomes will also be measured with ANOVA analysis.

Sample Size and Accrual

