We performed a pilot study of 25 patients to assess catheter related pain after transurethral resection of the prostate. Using this data, we calculated an average and standard deviation for catheter related pain of 3.2 and 2.45 respectively. In order to detect a difference in pain score of 0.6 between groups, at a power of 80% and alpha of 5%, we determined 44 patients should be included. Predicting a dropout rate of 20%, we plan to enroll approximately 55 patients to achieve 44 patients with full participation.

Data Monitoring

The Clinical Research Program will assess the risk of this trial and will devise and implement an internal monitoring and/or auditing plan for this trial. This plan will be revised as necessary during the life of the trial based upon a variety of factors, including but not limited to: protocol amendments, staff turnover, enrollment metrics, and compliance issues noted. An interim data analysis at 15 patients will be performed to assess pads per day, pain scores between groups, and assess for any difference in complications. If there is a significant difference in major post-operative complications, or patient safety concerns, the study will be terminated.

Data Analyses

Variables to be included in data analysis include aspects of the patient's history as outlined above. Additionally, operative details such as bladder neck reconstruction, change in technique from the stand running robotic vesico-urethral anastomosis or other significant alterations from the standard RALP approach will be included.

Outliers will be double-checked for accuracy. Subjects lost to follow-up will be included in short-term analysis only. Missing post-op data will be evaluated on a case-by-case basis with likely only long-term data being an issue. Missing operative data will be clarified with the operating surgeon. Any data that are not able to be collected with reasonable efforts will not be considered protocol deviations. Data analysis will specifically include risk ratios with 95% confidence intervals for those factors outlined above.

DATA COLLECTION

Records Keeping

Records and data will be kept using a password protected database. Paper source, including signed Informed Consent Form (ICF), will be stored in a secure location for the duration of the trial and securely archived for 10 years following study closure.

Secure Storage of Data

After data collection only de-identified data sets will be used for analysis and further study.

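### Surgeons set catheter-removal timing, but no balancing by surgeon is described and surgeon is not named in the ANOVA: a modest, cheaply reduced loss of precision and interpretability, not bias

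*Combined protocol and SAP*

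**What the plan says.** **Surgeons.** Patient recruitment: "Patients seen in pre-operative consultation by Virginia Mason Medical Center urologists will be assessed by the consulting surgeon". The plural implies more than one surgeon; the number who operate is not given.

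**What is left to the surgeon.** Timing of Data Collection says that timing of catheter "removal will be determined by the surgeon and is not affected by the study". The Schedule of Procedures records the day of removal.

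**Primary outcome.** Study Purpose and Objectives gives it as mean catheter-related pain on days 5 to 7. Data Collection Procedures has it collected on day 7, just before the catheter comes out.

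**Assignment and analysis.** Treatment Methodology and Statistical Considerations gives a 1:1 ratio and the Excel randomisation function. It mentions no blocks, strata or minimisation. It continues: "We will use an ANOVA statistical variance model to test the hypothesis that the 20Fr group will have a higher mean pain score". Secondary outcomes are also to be analysed by ANOVA. Data Analyses adds patient history and operative details; examples such as "change in technique from the stand running robotic vesico-urethral anastomosis or other significant alterations from the standard RALP approach will be included". Surgeon is not named there, though the list is open-ended.

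**Size.** Sample Size and Accrual: about 55 enrolled, so that 44 have full participation.

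**The concern.** Catheter pain on days 5 to 7 depends partly on whether the catheter is still in place for the whole window. If one surgeon tends to remove earlier than another, their patients may score differently for reasons unrelated to catheter size. In a large trial these differences average out across arms. With about 44 evaluable patients, one surgeon's patients can fall mainly in one arm, and the realised contrast then mixes catheter size with surgeon.

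At stake are the precision of the estimate and how readily the single realised result can be interpreted. If surgeons differ, that variation also stays in the error term of an ANOVA on catheter size alone.

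**Working it through.** **The plan's own figure.** The inputs are "In order to detect a difference in pain score of 0.6 between groups", with SD 2.45, 80% power and alpha 5%. Two-sided, n per arm = 2 × (1.960 + 0.842)² × 2.45² / 0.6² = 2 × 7.849 × 6.0025 / 0.36 = 261.7, so 262 per arm (524 in total). One-sided it is 207 per arm. The stated total of 44 is not reproduced; the dropout step is (44 / 0.8 = 55). That is a separate matter. Below, 44 is used only as the planned number of evaluable patients.

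**Assumptions not in the documents.** One surgeon has 15 of the 44 patients; that surgeon's patients differ from the rest by 1 pain point; as an alternative, the between-surgeon share of variance (ICC) is 0.05 to 0.20.

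**1. Chance of a 10:5 split or worse for that surgeon.**
- Independent draws, Binomial(15, 0.5): 2 × P(X ≤ 5) = 2 × 4,944 / 32,768 = 0.302.
- Fixed 22:22 list, hypergeometric (15 drawn from 44, of which 22 are in each arm): 2 × P(X ≥ 10) = 0.203.

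The protocol does not say which describes the Excel procedure. With three surgeons of nearly equal caseload (15, 15, 14), at least one has two thirds or more of their patients in one arm in 60% of independent-draw lists and 36% of fixed lists (simulation, 100,000 lists each).

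**2. What such a split does.** At 22 per arm, shift = (10/22 − 5/22) × 1 = 5/22 = 0.23 points. Against the 0.6-point target this is 0.227 / 0.6 = 38%. Against the standard error of the difference, 2.45 × √(2/22) = 0.739, it is 0.31 of one standard error.

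**3. Range over the surgeon effect.** For k equal-sized surgeons and a fixed 22:22 list, SD of the chance shift = √[ICC × 2.45² × (1 − 1/k) × (44/43) × (2/22)].

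| k | ICC 0.05 | ICC 0.20 |
|---|---|---|
| 2 | 0.12 | 0.24 |
| 3 | 0.14 | 0.27 |
| 5 | 0.15 | 0.30 |

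In simulation (40,000 trials per setting; 2, 3 and 5 surgeons) the shift exceeds 0.3 points in 3–5% of trials at ICC 0.05 and 15–27% at ICC 0.20. It exceeds 0.6 points in at most about 5%. Type I error of the unadjusted test is 4.9–5.2%.

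**4. What adjustment gains.** A 1-point effect in 15 of 44 patients has variance (15/44) × (29/44) × 1² = 0.225, which is 0.225 / 6.0025 = 3.7% of the total. Against this, chance imbalance costs precision: with a fixed list, the expected R² of arm on surgeon is (levels − 1) / 43.
- Two levels: variance ratio about (1 − 0.037) / (1 − 1/43) = 0.99, a slight gain.
- Three levels: about (1 − 0.037) / (1 − 2/43) = 1.01, a slight loss.

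Blocking within surgeon largely removes this cost. With residual SD 2.45 × √(1 − ICC), two-sided power at 22 per arm for 0.6 points rises from 12.6% to 13.0%, 13.5% and 14.6% at ICC 0.05, 0.10 and 0.20.

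**The case against.** **Delegation is narrow.** A reader might infer that background care as a whole is left to each surgeon. The text does not say so. Only removal timing is delegated. Study design makes significant deviation from the operative protocol a screen failure without randomisation, and Data Analyses refers to a standard approach. On the analgesic regimen the text is silent, which is not delegation. This objection stands.

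**Removal timing is partly bounded.** Pain is to be collected just before removal, an expected duration over 14 days is an exclusion, and an actual duration over 14 days may lead to discontinuation. These limits bear on late removal. They do not rule out removal before the days 5 to 7 window closes, so the point survives in part.

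**Silence is not exclusion.** The Excel function could shuffle a fixed list, and the operative-details list could be read to include surgeon. Both are fair. They are also reasons to write the method and the model down before results are seen.

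**Chance imbalance is not bias.** A reader might infer that the comparison is biased or its test invalid. Under valid randomisation it is not: type I error stays near 5%. Nor does an uneven overall split matter much. At 18:26 the standard error is 2.45 × √(1/18 + 1/26) = 0.751, against 0.739 at 22:22. A claim that every outcome shifts together would need the same surgeon to differ on all of them, and nothing in the documents shows this.

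**Blocking has a price.** Surgeons judge intraoperative screen failure, and no masking is described. A short blocked list per surgeon makes the next assignment easier to guess. This stands as a cost of the remedy.

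**Conclusion.** The point holds as a cheap improvement. Removal timing, which can affect the primary outcome, is set by surgeons; more than one surgeon is implied; and neither assignment nor analysis is stated to account for them. A marked imbalance for one surgeon is plausible under either reading of the Excel procedure. Its likely effect on the pain difference is a fraction of one standard error.

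The size rests on the number of surgeons, their caseloads and how far their patients differ, none of which the documents give. If surgeons hardly differ, nothing is gained and a little precision may be lost. A reader might also hope that adjusting for surgeon makes 44 patients enough; power of 13.0–14.6% shows that it does not.

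**What to change.** 1. In Treatment Methodology and Statistical Considerations, state the number of operating surgeons and how the Excel list is made (independent draws or a fixed list).
2. Pre-specify operating surgeon as a factor in the ANOVA, pooling low-volume surgeons by a rule set before results are seen, so that only two or three levels are used. Cost: a sentence, one or two degrees of freedom, and a possible slight loss of precision if surgeons hardly differ.
3. For patients still to be assigned, use permuted blocks of randomly varying size within the same surgeon groups. Cost: a short list per group and some predictability of assignment, which varying block sizes limit. If assignment is complete, only items 1, 2 and 4 apply.
4. Report the day of catheter removal, already recorded, by arm. It arises after assignment, so it is better described than used as an adjustment variable. Cost: one table row.

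None of this changes clinical management. The sample-size calculation needs its own correction.

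### ANOVA is assigned to every secondary outcome, including yes/no complications, and the promised risk ratios have no stated outcome or zero-event rule, so the main harm comparison may end with no usable estimate

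*Combined protocol and SAP*

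**What the plan says.** The combined protocol and SAP, under Treatment Methodology and Statistical Considerations, assigns ANOVA to the primary pain score and continues: "Secondary outcomes will also be measured with ANOVA analysis". No outcome is excepted.

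The list of secondary outcomes under Study Purpose and Objectives has six items. Five are numeric: IPSS and QoL scores, opioid use, pads per day, flow rate and post-void residual. The sixth is not: "Long-term complications at 12 weeks, 1 and 2 years". Bladder neck contracture is the example given.

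Data Analyses adds one more method: "Data analysis will specifically include risk ratios with 95% confidence intervals for those factors outlined above". That section opens with "Variables to be included in data analysis include aspects of the patient's history as outlined above" and goes on to operative details. What the ratios compare, and for which outcome, is not stated.

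The plan gives no method for binary or sparse outcomes, no rule for an arm without events, and no expected complication rate. It gives only a direction: more bladder neck constriction is anticipated with the 16 Fr catheter.

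**The concern.** Complications are the harm side of the catheter-size question. The protocol predicts more bladder neck constriction in one arm, justifies the two-year follow-up by the need to evaluate complications, and collects no other study data at 1 and 2 years.

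ANOVA compares means using a pooled within-group variance. On 0/1 data that variance is zero when no patient has an event, and the F statistic becomes 0/0. A risk ratio with the usual logarithmic interval breaks down sooner: one empty arm is enough. In a trial of this size either could happen at realistic rates. The team would then have to choose a method after seeing the data, or report the main safety comparison without an interval.

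**Working it through.** **Inputs from the documents.** Sample Size and Accrual: "at a power of 80% and alpha of 5%, we determined 44 patients should be included". Allocation is 1:1, so 44 / 2 = 22 per arm. The dropout step reproduces: 44 / 0.8 = 55 enrolled. The 44 itself does not follow from the stated difference of 0.6 and SD of 2.45, which need about 262 per arm (2 × (1.960 + 0.842)² × 2.45² / 0.6² ≈ 262, two-sided). That is a separate matter. I use 22 per arm because it is the size the plan states.

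**Assumption.** The true complication rate p per arm is not given. I use 1% to 20%, equal in both arms unless stated.

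**Step 1. How often each method cannot be computed.**

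- Risk ratio or its interval undefined (at least one arm with no events): 1 − (1 − (1 − p)²²)². At p = 5%: 0.95²² = 0.324, and 1 − 0.676² = 0.54.
- ANOVA not computable (no events in either arm): (1 − p)⁴⁴. At p = 5%: 0.95⁴⁴ = 0.105.

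| Assumed rate per arm | Risk ratio or interval undefined | ANOVA not computable | F-test type I error |
|---|---|---|---|
| 1% | 96% | 64% | <0.1% |
| 2% | 87% | 41% | 0.1% |
| 5% | 54% | 10% | 1.5% |
| 10% | 19% | 1.0% | 4.3% |
| 20% | 1.5% | <0.1% | 5.1% |

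The last column comes from exact enumeration of all tables at 22 v 22. Its maximum over rates up to 50% is about 5.2%.

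**Step 2. Other arm sizes.** Patients lost to follow-up leave the long-term analysis, so the arms may be smaller at 1 and 2 years. At 17 per arm and 5%, the ratio or its interval is undefined in 66% of trials. If nearly all 55 enrolled patients stayed (27 per arm), it is still 44%.

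**Step 3. What a defined risk ratio shows.** The log-scale standard error is √(1/a − 1/22 + 1/b − 1/22) for a and b events.

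- 1 v 1: √1.909 = 1.382; interval exp(±1.96 × 1.382) = 0.07 to 15.0.
- 3 v 1: √1.242 = 1.115; ratio 3.0, interval 0.34 to 26.7.

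These intervals are valid but say very little.

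**Step 4. What a score-based risk difference shows (Newcombe, 22 v 22).**

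- 0 v 0: the Wilson upper limit for 0/22 is 3.84 / (22 + 3.84) = 14.9%, so the difference is 0 with interval −14.9 to +14.9 points.
- 1 v 0: −10.8 to +21.8 points.
- 4 v 0: −0.2 to +38.5 points.

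The risk ratio or its interval is undefined in all three tables; the risk difference has a finite interval in each.

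**The case against.** The two analysis sentences can be read together as ANOVA for means and risk ratios for events. That is a sensible reading, but the plan does not state it: the ANOVA sentence has no exception and the risk-ratio sentence names no outcome. Even on that reading, no rule covers an empty arm.

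The rarity of events is assumed. Complications are defined broadly, so a pooled rate could be higher, and at 20% per arm both methods mostly work. This stands as a limit on the size of the problem. It helps less for bladder neck contracture taken alone.

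Three stronger readings are tempting, and the documents do not support them.

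- A reader might infer that ANOVA intervals would be far too narrow. If a 95% interval for the difference is built from the pooled variance, its coverage at 22 v 22 is 79% for 5% v 2%, 73% for 5% v 1% and 49% for 2% v 1%. Nearly all of that loss comes from 0 v 0 tables, where ANOVA cannot be computed anyway. Without them coverage is 99.3%, 98.7% and 99.8%, and at higher rates the loss is at most modest (92.4% at 10% v 5%). The plan does not promise such an interval; the only intervals it names are for risk ratios, which are wide when defined.
- A reader might infer false positives, since 4 v 0 gives p = 0.037 by ANOVA and 0.108 by Fisher's exact test. With the F-test's size at most about 5.2%, the gap mainly reflects Fisher's conservatism: its size is 0.3% at 5% per arm and 2.4% at 20%.
- A reader might infer that risk ratios are promised for IPSS, pads or flow rate. The sentence follows patient history and operative details and does not mention those outcomes. It is unclear, not plainly wrong.

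It is also fair to say that complications are one of six secondary items and that the primary analysis is unaffected.

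**Conclusion.** The point holds as a gap in the plan for complications. ANOVA is assigned to a yes/no outcome, and the only alternative has no stated outcome and no zero-event rule. At 22 per arm, if rates are about 5% or less, the risk ratio or its interval is undefined in 54% or more of trials, and ANOVA cannot be computed in 10% (at 5%) to 41% (at 2%). Where the ratio is defined, a handful of events gives an interval too wide to interpret.

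The consequence is a missing or uninformative safety estimate, not an inflated false-positive rate or false precision. The size rests on the assumed rates and on the stated 44 evaluable patients. At 10% per arm the undefined share falls to 19%, and at 20% it is negligible. The numeric secondary outcomes are not affected by this point.

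**What to change.** Replace the sentence on secondary outcomes with wording to this effect:

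- IPSS, QoL, opioid use, pads per day, flow rate and post-void residual: difference in means with 95% confidence interval, from ANOVA.
- Complications at 12 weeks, 1 year and 2 years: number and percentage of patients by arm, and the risk difference with a score-based 95% confidence interval. Name one method, Newcombe or Miettinen-Nurminen.

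In Data Analyses, state that the risk ratios compare the catheter groups on complications and are reported only when both arms have events.

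Fisher's exact test may be added but need not be. It is conservative, and at 20% v 5% it lowers the power to detect a difference from 33% to 20%, which matters for a harm outcome.

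The cost is wording only, with no new data or patients. Intervals will be somewhat wider than pooled-variance ones when events are sparse: at 1 v 0, −10.8 to +21.8 points against −4.6 to +13.7. That width is a fair statement of what 22 patients per arm can show.
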